CBEU	Cytobacteriological Examination of Urine
CI	Confidence Interval
CS	Clinically significant
DBL	Data Base Lock
ECG	Electrocardiogram
eCRF	Electronic Case Report Form
FAS	Full Analysis Set
GFR	Glomerular Filtration Rate
IMP	Investigational Medical Product
LLN	Lower Limit of Normal reference
LLOQ	Lower Limit of Quantification
MCMC	Markov Chain Monte Carlo
MITOS	Amyotrophic Lateral Sclerosis-Milano-Torino staging system
NCS	Non-Clinically Significant
NFL	Neurofilament Light Chain
QoL	Quality Of Life
PK	Pharmacokinetics
PPS	Per Protocol Set

STATISTICAL ANALYSIS PLAN		
InFlectis BioScience	Sponsor:	InFlectis BioScience
	Protocol Number:	P288ALS
VERSION 1.0 NOV 12, 2024		

SAP	Statistical Analysis Plan
SD	Standard Deviation
SE	Standard Error
SS	Safety Set
SVC	Slow Vital Capacity
TAESI	Treatment Adverse Event of Specific Interest
TEAE	Treatment Emergent Adverse Event
TFL	Table, Figure, Listing
RS	Randomized Set
ULN	Upper Limit of Normal reference
ULOQ	Upper Limit of Quantification

STATISTICAL ANALYSIS PLAN		
InFlectis BioScience	Sponsor:	InFlectis BioScience
	Protocol Number:	P288ALS
VERSION 1.0 NOV 12, 2024		

VERSION HISTORY

Version	Version Date	Changes	Author
1.0			

1 INTRODUCTION

It has been demonstrated that targeting the unfolded protein response (UPR) pathway, in particular the phosphatase complex protein phosphatase 1 regulatory subunit 15A/protein phosphatase 1c (PPP1R15A/PP1c) could be beneficial to ALS patients. IFB-088 is a PPP1R15A/PP1c phosphatase complex inhibitor that has demonstrated activity in the so far best studied animal model of ALS, i.e. transgenic rodents overexpressing the gene encoding superoxide dismutase 1 (SOD-1). Similarly, another PPP1R15A/PP1c phosphatase complex inhibitor, guanabenz, also demonstrated benefits in ALS animal models. The 2 molecules have the same pharmacological target but guanabenz also exhibits α 2 adrenergic activity responsible for lowering blood pressure. IFB-088 has been shown to be devoid of this α 2 adrenergic activity and demonstrated a good safety profile in a phase I study in healthy volunteers as no toxicity signal has been detected at any doses evaluated, including single daily doses up to 60 mg and repeated daily doses up to 50 mg for 14 days. Guanabenz has been investigated in an exploratory phase II study in ALS patients. It showed encouraging results, especially in patients with bulbar-onset ALS. The incidence of hypotension in this study discouraged further development in ALS. Since a similar efficacy is expected for IFB-088 without hypotensive effects, an exploratory study has been designed to assess the safety and the efficacy of IFB-088 in patients with bulbar-onset ALS. P288ALS is a double-blind, placebo-controlled, exploratory randomised clinical trial to assess the safety and efficacy of IFB-088 plus riluzole 100 mg vs placebo plus riluzole 100 mg in patients with bulbar-onset amyotrophic lateral sclerosis.

2 STUDY OBJECTIVES, ENDPOINTS, AND ESTIMANDS

2.1 Objectives

2.1.1 Primary Objective

The primary objective is to assess the safety of IFB-088 50 mg/day in patients with bulbar-onset ALS.

2.1.2 Secondary Objectives

The secondary objectives are:

STATISTICAL ANALYSIS PLAN		
InFlectis BioScience	Sponsor:	InFlectis BioScience
	Protocol Number:	P288ALS
VERSION 1.0 NOV 12, 2024		

- To assess the efficacy of IFB-088 50 mg/day plus riluzole 100 mg/day versus placebo plus riluzole 100 mg/day over a 6-month period in patients with bulbar-onset ALS
- To determine pharmacokinetics (PK) parameters of IFB-088
- To investigate the effects of IFB-088 on ALS potential biomarkers
- To investigate quality of life (QoL).

2.2 Endpoints

2.2.1 Safety Endpoints

- Adverse Event (AE) and Treatment Emergent Adverse Event (TEAE)
- Laboratories parameters
- Vital signs
- ECG parameters

2.2.2 Efficacy Endpoints

- Change in Revised ALS functional rating scale (ALSFRS-R) score from baseline to month 3 and to month 6,
- Worsening according to ALS-Milano-Torino staging system (MITOS) score, i.e. progression to a higher stage at 6 months compared to the baseline,
- Change in King's College score from baseline to month 6,
- Assessment of respiratory function (slow vital capacity [SVC], sniff test [optional], arterial blood gases [ABG]): exploratory endpoint.
- Evaluation of nutritional status and body composition by bioelectrical impedance: exploratory endpoint

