	
Secondary objectives
 
 • To assess the efficacy of IFB-088 50 mg/day plus riluzole 100 mg/day versus placebo plus riluzole 100 mg/day over a 6-month period in patients with bulbar-onset ALS, • To determine pharmacokinetics (PK) parameters of IFB-088, • To investigate the effects of IFB-088 on ALS potential biomarkers, • To investigate quality of life (QoL). 
Secondary and exploratory endpoints
 
Efficacy:
 
 • Change in Revised ALS functional rating scale (ALSFRS-R) score from baseline to month 3 and to month 6, • Worsening according to ALS-Milano-Torino staging system (MITOS) score, i.e. progression to a higher stage at 3 and at 6 months compared to the baseline, • Change in King's College score from baseline to month 3 and to month 6, • Assessment of respiratory function (slow vital capacity [SVC], sniff test [optional], arterial blood gases [ABG]): exploratory endpoint. • Evaluation of nutritional status and body composition by bioelectrical impedance: exploratory endpoint 
PK parameters:
 
 • Plasma concentration of IFB-088 and IFB-139, • AUC of IFB-088 and IFB-139, • Maximum observed plasma concentration (C_{max}), with associated T_{max}, • Terminal or apparent terminal half-life ($t_{1/2}$), • Apparent systemic clearance, apparent volume of distribution. 
Biomarkers:
 
 • Change in TDP-43 plasmatic concentration from baseline to 6 months, compared to placebo, • Change in neurofilament (NfL) light chain and NfL heavy chain plasmatic concentration from baseline to 6 months, compared to placebo, • Change in plasmatic (neuro)inflammatory biomarkers from baseline to 3 months, and from baseline to 6 months, compared to placebo, • Change in plasmatic oxidative stress biomarkers from baseline to 3 months and from baseline to 6 months, compared to placebo. 
QoL:
 
 • Change in ALS assessment questionnaire (ALSAQ-40) from baseline to 6 months.
Study Population, Countries and sites:	Adult patients with bulbar-onset ALS. Patients will be recruited in France and in Italy.

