2. STUDY OBJECTIVES AND ENDPOINTS

Objectives	Endpoints
Primary	
To assess the safety of the test product, IFB-088 50 mg/day, in patients with bulbar-onset ALS.	
 Incidence, grade and relationship to IFB-088 for treatment emergent AEs, SAEs, and AESIs, AEs leading to dose interruption or premature discontinuation.
Secondary and exploratory	
 Change in ALSFRS-R score from baseline to month 3 and to month 6, Worsening according to ALS-MITOS score, i.e. progression to a higher stage at 3 and at 6 months compared to the baseline, Change in King's College score from baseline to month 3 and to month 6. 
Exploratory endpoints:
 
 Assessment of respiratory function (slow vital capacity [SVC], sniff test [optional], arterial blood gases [ABG]). Evaluation of nutritional status and body composition by bioelectrical impedance.
To determine the PK parameters of IFB-088.	
Measurements of PK parameters:
 
 Plasma concentration of IFB-088 and IFB-139, AUC of IFB-088 and IFB-139, Maximum observed plasma concentration (C_{max}), with associated T_{max}, Terminal or apparent terminal half-life ($t_{1/2}$), Apparent systemic clearance, apparent volume of distribution.

To investigate the effects of IFB-088 on potential biomarkers.	
 Change in TDP-43 plasmatic concentration from baseline to 6 months, compared to placebo, Change in neurofilament (NfL) light chain and NfL heavy chain plasmatic concentration from baseline to 6 months, compared to placebo, Change in plasmatic (neuro)inflammatory biomarkers from baseline to 3 months, and from baseline to 6 months, compared to placebo, Change in plasmatic oxidative stress biomarkers from baseline to 3 months and from baseline to 6 months, compared to placebo.
To investigate the QoL of ALS patients.	Change in ALS assessment questionnaire (ALSAQ-40) from baseline to 6 months.

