- Worsening (i.e. progression to a higher stage at 6 months compared to the baseline stage defined by ALS-MITOS score): the proportion of progressors will be compared between both treatment groups. The difference in binomial proportions will be estimated along with an exact 95% CI. A sensitivity Bayesian analysis using the historical placebo data from the ProMISe study [26] will be also performed and further detailed in the SAP. Progressors will also be analysed in a logistic regression model adjusting for treatment and additional relevant covariates (specified in the SAP). The treatment effect will be estimated in terms of an odds ratio associated with the 95% CI and p-value and also in terms of a difference in progression rates with its 95% CI using the method proposed by Ge and al. [45].
- Change in King's College score: the endpoint will be analysed with an approach similar to the analysis of ALS-MITOS score.

Analyses of the changes in efficacy endpoints from baseline to month 3 (as inferential analysis) and from month 3 to month 6 (as descriptive analysis) will be also proposed and further detailed in the SAP.

- Respiratory function: changes from baseline to 3 months and from baseline to 6 months will be analysed. Analyses will be further detailed in the SAP.
- Bioelectrical analysis: changes from baseline to 3 months and from baseline to 6 months will be analysed for the planned following parameters: phase angle, Z200/Z5 impedance ratio, skeletal muscle mass, dry mass, and dry mass without fat. Analyses will be further detailed in the SAP.

PK Analysis

Individual plasma concentrations of IFB-088 and IFB-139 (i.e. IFB-088 metabolite) with corresponding nominal sampling times, will be tabulated for each subject and scheduled sampling time, together with descriptive statistics. Mean plasma IFB-088 concentrations profiles by cohort will be presented over time graphically, using blood sampling time (x axis) and concentrations (y axis) on both linear and semi-log scales.

Derived and observed PK parameters will be evaluated by noncompartmental analysis. The following parameters will be listed and summarised by cohort, as appropriate:

- AUC, ng.h/mL,
- C_{max}, ng/mL, with associated T_{max}, h,

- Terminal or apparent terminal $t_{1/2}$, h,
- Apparent systemic clearance (Cl/F, L/h) and apparent volume of distribution (Vd/F, L) at steady state, where F is the overall oral bioavailability of IFB-088.

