5.2.21 Efficacy endpoints

- ALSFRS-R subscore:

Three subscores will be considered as follows:

- Bulbar subscore: sum of items 1-3
- Motor subcore: sum of items 4-9
- Respiratory subcore: sum of items 10-12

Subscore will be considered as missing if an item is missing.

Note: for motor subscore, item 5 will be considered at missing if item 5a and 5b are missing.

- Worsening (i.e. progression to a higher stage compared to baseline defined by ALS-MITOS score):

Non progression at 6 months (V4) and 3 (V3) months will be derived as follows:

- 0 if ALS-MITOS score is higher at 6 months (or 3 months) compared to ALS-MITOS score at baseline
- 1 if ALS-MITOS score is lower or equal at 6 months (or 3 months) compared to ALS-MITOS score at baseline
- Change in King's College score

Non progression at 6 months and 3 months will be derived as follows:

- 0 if King's College score is higher at 6 months (or 3 months) compared to baseline
- 1 if King's College score is lower or equal at 6 months (or 3 months) compared to baseline
- SVC: percentage of the predicted value for age and sex (%)

Percentage of the predicted value will be calculated according to the formula of predicted FVC in 'Multi-ethnic reference values for spirometry for the 3–95-yr age range: the global lung function 2012 equations' article of Quanjer.

STATISTICAL ANALYSIS PLAN		
InFlectis BioScience	Sponsor: Protocol Number:	InFlectis BioScience P288ALS
VERSION 1.0 NOV 12, 2024		

$$\% \text{ of the predicted value} = (\text{SVC} / M_{\text{predicted}}) * 100$$

Where

For man:

$$M_{\text{predicted}} = \exp(-11.2281 + 2.4135 * \ln(\text{Height in cm}) + 0.0865 * \ln(\text{Age}) + Mspline)$$

$$Mspline = 0.3298 - 1.1230 * (\text{Age}/100) + 2.8110 * (\text{Age}/100)^2 - 5.4811 * (\text{Age}/100)^3 + 3.5964 * (\text{Age}/100)^4 - 0.5884 * (\text{Age}/100)^5$$

For woman:

$$M = \exp(-10.4030 + 2.2633 * \ln(\text{Height in cm}) + 0.0234 * \ln(\text{Age}) + Mspline)$$

$$Mspline = 0.0745 + 0.6006 * (\text{Age}/100) - 1.0684 * (\text{Age}/100)^2 - 1.1308 * (\text{Age}/100)^3 + 0.9730 * (\text{Age}/100)^4 + 0.0643 * (\text{Age}/100)^5$$

For example, 40 years white man, height 185 cm, SVC of 5L:

$$\% \text{predicted value} = (5/5.79) * 100 = 86 \%$$

For example, 35 years white woman, height 170 cm, SVC of 2.5L:

$$\% \text{predicted value} = (2.5/4.16) * 100 = 60 \%$$

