5.11.3.2.3 Descriptive analysis

In addition, a descriptive summary of observed MITOS stage values at baseline, Month 3 and Month 6 as well as their change from baseline to month 3 and to month 6 will also be provided.

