7 CHANGES TO PLANNED PROTOCOL ANALYSIS

Changes to planned protocol analysis are the following:

- Modification of the primary analysis of the primary efficacy endpoint. Modification of the imputation method for missing data due to deaths occurring during the study. The ANCOVA model will be used instead of the MMRM to account for different sources of missing data.
- Deletion of the Bayesian analysis. A Bayesian analysis was planned in the protocol to combine prior data from literature (Promise study) with current study data. However, as the populations differ (all-comers ALS patients in the Promise study vs bulbar-onset ALS patients only in P288ALS study), this Bayesian analysis will be further considered in a *post hoc* manner if appropriate.

STATISTICAL ANALYSIS PLAN		
InFlectis BioScience	Sponsor:	InFlectis BioScience
	Protocol Number:	P288ALS
VERSION 1.0 NOV 12, 2024		

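### The SAP drops the Month 3 between-arm comparison of MITOS and King's staging that the protocol planned as inferential, and does not list the change

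*SAP*

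**What the plan says.** **Protocol.** The synopsis and section 2 define MITOS worsening as "progression to a higher stage at 3 and at 6 months compared to the baseline". Section 2 defines the King's endpoint as "Change in King's College score from baseline to month 3 and to month 6". In section 8.1.5.2, King's has no separate method: "the endpoint will be analysed with an approach similar to the analysis of ALS-MITOS score", which means proportions of progressors. Directly after the ALSFRS-R, MITOS and King's bullets, the same section announces "Analyses of the changes in efficacy endpoints from baseline to month 3 (as inferential analysis". It contrasts this with a descriptive Month 3 to Month 6 analysis and leaves the details to the SAP.

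**SAP.** Section 2.2.2 keeps Month 3 for ALSFRS-R but words MITOS as "progression to a higher stage at 6 months compared to the baseline" and King's as change to Month 6. Section 5.2.21 nevertheless states for MITOS "Non progression at 6 months (V4) and 3 (V3) months will be derived as follows" and does the same for King's. Tables 2 and 3 and sections 5.11.3.2.1 and 5.11.4.2.1 compare the arms at Month 6 only. At Month 3, section 5.11.3.2.3 gives "a descriptive summary of observed MITOS stage values at baseline, Month 3 and Month 6", together with changes from baseline to both visits. Section 5.11.4.2.3 does the same for King's. Section 7 opens with "Changes to planned protocol analysis are the following" and lists two items: the new ALSFRS-R model with its imputation rules, and the removal of the Bayesian analysis.

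**The concern.** If the SAP is followed as written, the report will contain no between-arm estimate, interval or test for staging at Month 3, although the protocol promised an inferential analysis there. Three features suggest an oversight. The Month 3 variable is still derived and then never used. ALSFRS-R keeps its Month 3 comparison in 5.11.2.3 under the same protocol sentence. The section written to record departures from the protocol is silent.

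What is at stake is the planned Month 3 result for two secondary endpoints, and the ability of a later reader to tell whether it was left out by decision or by accident.

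**Working it through.** The point is textual, so the main check sets the documents side by side.

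| | ALSFRS-R | MITOS | King's |
|---|---|---|---|
| Month 3 endpoint in protocol section 2 | yes | yes | yes |
| Month 3 in SAP 2.2.2 | yes | no | no |
| Month 3 non-progression derived in SAP 5.2.21 | not applicable | yes | yes |
| Arms compared at Month 3 in the SAP | yes (5.11.2.3) | no | no |
| Month 3 descriptive summary in the SAP | yes | yes (5.11.3.2.3) | yes (5.11.4.2.3) |
| Loss of the Month 3 comparison listed in SAP 7 | nothing lost | no | no |

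**Does the protocol's Month 3 sentence cover staging?** It speaks of efficacy endpoints in general and follows the bullets for all three scales. Both staging endpoints are themselves defined at Month 3. King's is worded as a change but is to be analysed like MITOS, so progression at Month 3 is a fair reading for both.

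**Does the descriptive table stand in for the comparison?** No. It provides no difference, ratio or interval. SAP 5.11.1.3 leaves missing data unreplaced in descriptive analyses, so deaths and drop-outs before V3 fall out of it. At Month 6 they are counted as progressed.

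**How many results are lost?** Two scales × two measures (difference and ratio, as in Tables 2 and 3) = 4 estimates.

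**How precise would they be?** The protocol's total reproduces: 42 / (1 − 0.15) = 49.4, so 50 randomised. At 2:1 this is 50 × 2/3 = 33.3 and 50 × 1/3 = 16.7, or about 33 and 17. The documents give no staging rates. Assuming non-progression of 80% and 60%:

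- SE = √(0.80 × 0.20 / 33 + 0.60 × 0.40 / 17) = √(0.00485 + 0.01412) = 0.138
- 95% half-width = 1.96 × 13.8 = about 27 points

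One placebo patient reclassified moves the placebo rate by 1/17 = 5.9 points.

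**Illustration of the missing-equals-progressed rule.** If a proportion m is missing in both arms, unrelated to stage, the expected difference is (1 − m) × the true difference. For an assumed true difference of 20 points:

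- Month 6, m = 15% (the protocol's drop-out rate): 0.85 × 20 = 17.0 points
- Month 3, m = 7.5% (assuming half of drop-outs occur by then): 0.925 × 20 = 18.5 points

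The gap is 1.5 points.

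**The case against.** The strongest reply is that little is lost. The trial is exploratory, its primary objective is safety, and efficacy is neither powered nor adjusted for multiplicity. The protocol's detailed MITOS method is written for Month 6, with Month 3 left to the SAP. Stage changes at Month 3 are still summarised, and for King's a change is literally what the endpoint names. All of this stands and limits the severity. It does not remove the discrepancy: leaving details to the SAP is not permission to turn an analysis announced as inferential into a descriptive one without saying so.

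A reader might infer more than the documents support, in three ways.

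- **That the two endpoints go unanswered.** They do not. Month 6 is compared on the FAS and again on the PPS, and Month 3 stages and changes are tabulated.
- **That Month 3 would show whether a Month 6 difference is due to drop-out.** It cannot. A difference at Month 6 without one at Month 3 is also what later progression would produce. The Month 6 missing-data rule is a separate choice and does not follow from the Month 3 omission. For MITOS, counting a death as progression follows the scale, where death is stage 5. The observed Month 6 stages and the PPS repeat, which leans towards patients present at V4, already give a partial check at the right time point.
- **That the dilution figures measure how serious this is.** Only the 15% comes from the protocol. The rest assumes a 20-point effect, the same at both visits, and half of drop-outs by Month 3. Even then the 1.5-point gain is small beside a half-width of about 27 points.

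**Conclusion.** The concern holds as an undeclared downgrade. The protocol planned an inferential Month 3 analysis for MITOS and King's. The SAP removes Month 3 from both endpoint definitions, derives a variable that feeds no stated analysis, and does not record the change. The size is the Month 3 comparison of two secondary endpoints (four estimates).

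This rests on the wording of the documents, including the reading that the protocol's Month 3 sentence covers both staging scales and that King's is analysed as progression. It does not rest on any assumed rate. The half-width and dilution figures are illustrations only. The Month 6 analyses and the safety objective are unaffected. The correction should be made, chiefly because it restores a planned result at very little cost.

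**What to change.** Before unblinding:

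1. In SAP 2.2.2, restore Month 3 for MITOS worsening and King's change.
2. In SAP 5.11.3 and 5.11.4, add for V3 on the FAS the non-progression rate by arm, with the difference and ratio and their confidence intervals, by the Month 6 method and from the 5.2.21 variable.
3. State the V3 missing-data rule: as at Month 6, deaths and drop-outs before V3 count as progressed. A discontinuation visit that 5.2.5 maps to V3 (days 83 to 99) is an observed value. Say also how a patient with no V3 stage but an observed V4 stage is handled, because that pattern can arise only at Month 3.
4. As a low-cost aid to reading the results, show per arm at each time point how many progressors are observed stage increases, deaths and other missing values. The protocol does not require this, but it is useful when one placebo patient is worth about 6 points.

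The cost is four estimates and one small count table, with the matching table shells. No new data are needed, and there is no multiplicity scheme to disturb. SAP section 5 requires an addendum for changes after final database lock, which is a reason to settle this earlier. If the sponsor prefers to keep Month 3 staging descriptive, section 7 should say so and give the reason, though the planned comparison would then still be lost.

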2.3 Estimands

Table 1. Change in ALSFRS-R from baseline to month 6 (V4)

Objective: To estimate the treatment effect (IFB-088 vs. placebo), on the Change in ALSFRS-R assessed at Month 6.
Estimand: Treatment-Policy Strategy
Treatment: IFB-088 or matching placebo

STATISTICAL ANALYSIS PLAN		
InFlectis BioScience	Sponsor: Protocol Number:	InFlectis BioScience P288ALS
VERSION 1.0 NOV 12, 2024		

ESTIMAND	ANALYSIS
Target population	Analysis set
Patients with bulbar-onset amyotrophic lateral sclerosis	Full Analysis Set (FAS) defined as all randomized subjects who received at least one dose of study treatment (even if discontinued prematurely) with non-missing baseline ALSFRS-R value.
Variable	Outcome measure
Change in ALSFRS-R assessed at Month 6	Mean change
Handling of intercurrent events	Handling of missing data

 • Death related to disease progression • Death not related to disease progression. • Drop-out 
Treatment policy will be applied.
	
 • Estimand #1 (primary estimand): Missing data will be handled depending on the type of the intercurrent event (i.e.). - Missing data due to deaths: 
 a) due to disease progression: the ALSFRS-R score at month 6 will be imputed by the worst value (i.e. 0) b) other reason (sudden death included): 
 - if the ALSFRS-R score is not missing at Month 3, the ALSFRS-R score at month 6 will be imputed by linear extrapolation given baseline and Month 3 ALSFRS-R score available values. Note: in the linear extrapolation at month 6, the timepoint of ALSFRS assessment considered at V3 will be the exact calendar date of V3 assessment. Calendar time of V4 will be considered as 180 days. - if the ALSFRS-R score is missing at Month 3, the ALSFRS-R score at month 6 will be imputed by linear extrapolation based on the predicted value in the linear regression model including terms for intercept and baseline ALSFRS-R score estimated within the treatment group to

STATISTICAL ANALYSIS PLAN		
InFlectis BioScience	Sponsor:	InFlectis BioScience
	Protocol Number:	P288ALS
VERSION 1.0 NOV 12, 2024		

	
which the patient is randomized. Imputed values will be rounded to the nearest integer. Imputed value higher than 48 will be replaced by 48 and imputed value lower than 0 will be replaced by 0.
 
 - Missing data due to drop-outs or withdrawal will be imputed with the same approach used for handling missing data due to deaths for reasons not related to disease progression. Imputed values will be rounded to the nearest integer. Imputed value higher than 48 will be replaced by 48 and imputed value lower than 0 will be replaced by 0. • Estimand #2: Missing data will be handled depending on the type of the intercurrent event (i.e.). 
 - Missing data due to deaths, whatever the cause: the ALSFRS-R score at month 6 will be imputed by the worst value (i.e. 0). - Missing data due to drop-outs or withdrawal will be imputed with the same approach as for Estimand #1 used for handling missing data due to deaths not related to disease progression. Imputed values will be rounded to the nearest integer. Imputed value higher than 48 will be replaced by 48 and imputed value lower than 0 will be replaced by 0. • Estimand #3: Missing data will be handled depending on the type of the intercurrent event (i.e.). 
 -Missing data due to death whatever the cause: the ALSFRS-R score at month 6
--	--

STATISTICAL ANALYSIS PLAN		
InFlectis BioScience	Sponsor: Protocol Number:	InFlectis BioScience P288ALS
VERSION 1.0 NOV 12, 2024		

	
will be imputed by the worst value (i.e. 0).
 
-Missing data due to drop-outs or withdrawal will be replaced by multiple imputation assuming Missing at random and monotone regression. Note: model for multiple imputation will be done without patient who died before V4.
 
Imputed values will be rounded to the nearest integer.

Population-level summary measure	Analysis approach

Difference in LS mean changes between IFB-088 and placebo
 
Hodges-Lehmann estimate of the difference between IFB-088 and placebo
	
An analysis of covariance (ANCOVA) model of change from baseline in ALSFRS-R Score to month 6 will be fitted. Adjusted LS means and 95% confidence interval for each treatment group and the difference in LS means along with 95% confidence interval and p-value will be estimated in this ANCOVA model.
 
Estimand # 1 will be considered primarily.
 
Sensitivity analyses considering Estimands # 2 and # 3.
 
Supportive analysis will be performed on the PPS, considering Estimand # 1
 
A non-parametric analysis on the FAS will be performed considering Estimand #1.
 
The Hodges-Lehmann estimate along with the 95% CI and Wilcoxon p-value will be provided.

Table 2: Change in MITOS stage from baseline to month 6 (V4)

Objective: To estimate the treatment effect (IFB-088 vs. placebo), on the change in MITOS stage from baseline to Month 6 (V4).
Estimand: Treatment-Policy Strategy
Treatment: IFB-088 or matching placebo

STATISTICAL ANALYSIS PLAN		
InFlectis BioScience	Sponsor: Protocol Number:	InFlectis BioScience P288ALS
VERSION 1.0 NOV 12, 2024		

ESTIMAND	ANALYSIS
Target population	Analysis set
Patients with bulbar-onset amyotrophic lateral sclerosis	Full Analysis Set (FAS) defined as all randomized subjects who received at least one dose of study treatment (even if discontinued prematurely) with non-missing baseline value.
Variable	Outcome measure
Binary endpoint. Progression is defined as a MITOS stage higher at month than at baseline	Percentage of patients who did not progress to a higher MITOS stage at 6 months compared to baseline.
Handling of intercurrent events	Handling of missing data

 • All -cause deaths • Drop-out Treatment policy will be applied.	Estimand #1 Missing data at month 6 for whichever reason will be considered as progression.
Population-level summary measure	Analysis approach
Difference in non-progression rates at month 6 between IFB-088 and placebo Non-progression rate ratio at month 6 between IFB-088 and placebo .	Difference in rates of non-progressors at month 6 (according to change in MITOS stage) between IFB-088 vs placebo along with 95% CIs estimated according to the binomial exact method. Ratio of rates of non-progressors at month 6 (according to change in MITOS stage) between IFB-088 vs placebo along with 95% CIs estimated according to the binomial exact method. Supportive analysis will be performed on the PPS

Table 3: Change in King's College stage from baseline to month 6 (V4)

Objective: To estimate the treatment effect (IFB-088 vs. placebo), on the change in King's College stage from baseline to Month 6 (V4).	
Estimand: Treatment-Policy Strategy	
Treatment: IFB-088 or matching placebo	
ESTIMAND	ANALYSIS

STATISTICAL ANALYSIS PLAN		
InFlectis BioScience	Sponsor: Protocol Number:	InFlectis BioScience P288ALS
VERSION 1.0 NOV 12, 2024		

Target population	Analysis set
Patients with bulbar-onset amyotrophic lateral sclerosis	Full Analysis Set (FAS) defined as all randomized subjects who received at least some dose (even if discontinued prematurely) with no missing value at baseline.
Variable	Outcome measure
Binary endpoint. Progression is defined as a King's College stage higher at month 6 than at baseline	Percentage of patients who did not progress to a higher King's College stage at 6 months compared to baseline
Handling of intercurrent events	Handling of missing data

 • All -cause deaths • Drop-out 
Treatment policy will be applied.
	
Estimand #1
 
Missing data at month 6 for whichever reason will be considered as progression.

Population-level summary measure	Analysis approach

Difference in non-progression rates at month 6 between IFB-088 and placebo
 
Non-progression rate ratio at month 6 between IFB-088 and placebo
	
Difference in rates of non-progressors at month 6 between IFB-088 vs placebo according to King's College along with 95% CIs estimated according to the binomial exact method.
 
Ratio of rates of non-progressors at month 6 between IFB-088 vs placebo according to King's College along with 95% CIs estimated according to the binomial exact method
 
Supportive analysis will be performed on the PPS

STATISTICAL ANALYSIS PLAN		
InFlectis BioScience	Sponsor:	InFlectis BioScience
	Protocol Number:	P288ALS
VERSION 1.0 NOV 12, 2024		

